8.1 Extent of Exposure

The treatment duration (in days) and the study duration (in days) will be calculated as follows:

- date of last administered vaccine date of first vaccination + 1
- date of last attended visit date of signed Informed consent + 1

The treatment duration as well as the study duration will be tabulated (summary statistics). A data listing will be provided.

8.2 Study medication

The study medication will be prepared at site and administered during the study visits. Each treatment will be documented in the subject's charts, the eCRF and an IMP Inventory Log (CSP section 5.8). A data listing of study medication details will be provided.

8.3 Adverse Events

Adverse Events are statistically analyzed once for the Preliminary Analysis up to Visit 3 and once for the final analysis.

The Preliminary Analysis includes all Adverse Events with a start date which is at of before the date of Visit 3. Adverse Events will be coded using the Medical Dictionary for Regulatory Activities (cp. section 2.15)

Solicited AEs comprise reactions at the injection site or systemic reactions that are typical for vaccinations:

- Solicited local AEs (injection site reactions) are the following: injection site pain, tenderness, pruritus, erythema (redness), edema, induration (hardening)
- Solicited systemic AEs are the following: headache, fever, myalgia, limb discomfort, arthralgia, flu-like symptoms, nausea, vomiting, rash and excessive fatigue.

For solicited local and systemic AEs were summarized for a 7 day period. Solicited AEs will not be coded into MedDRA and no assessment of relatedness was performed.

An AE is considered to be related to study drug if the "Causal relationship to study treatment" was considered "definite", "probable", "possible" or the classification is missing.

For solicited local and systemic AEs the following tables will be tabulated:

- at least one AE
- at least one serious AE
- at least one severe AE

SAP (MV-CHIK-202, FINAL 3.0, 09-May-2018) Page 32 of 47 Based on: STAT03_A Statistical Analysis Plan Version 5.0, Effective Date 16-Dec-2016 Confidential and intellectual property of Assign DMB. No part of this document or its contents may be duplicated, referenced, published or otherwise disclosed in any form or by any means without prior written consent of Assign DMB.

• at least one AE by severity

An AE is considered to be a treatment-emergent AE (TEAE) if, and only if, first onset or worsening is simultaneous with or after first vaccination (AE start date is greater or equal first vaccination date). AEs for which it cannot be clearly decided if the start date was before or on/after first vaccination will be considered treatment-emergent, following a worst case approach.

For unsolicited AEs the following tables will be tabulated:

- at least one TEAE
- at least one severe TEAE
- at least one serious TEAE
- at least one TEAE related to study drug
- at least one medically attended TEAE
- at least one TEAE where an action was taken (i.e. no action taken was NOT ticked)
- at least one TEAE of special interest (arthritis)

The same tables grouped by SOC and PT will be provided.

Statistical analysis will be performed as described in section 2.7.3.

The following further summary tables will be provided:

- Number of subjects with solicited adverse event by symptom and severity -- MV-CHIK vs. control
- Number of subjects with unsolicited adverse event by symptom and severity -- MV-CHIK vs. control, for the five most frequent adverse events

The following listings will be provided:

- All AEs (including information if local/ systemic solicited, unsolicited)
- Solicited local adverse events
- Systemic adverse events
- Unsolicited adverse events
- Serious adverse events (SAEs)
- AEs leading to death

The following figures will be provided:

- Bar chart for number of subjects with solicited adverse event by event and maximum severity
- Bar chart for number of subjects with unsolicited adverse event by preferred term and maximum severity, where only the five most frequent terms will be included

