Solicited and non-solicited adverse events (AEs) were reported separately. Solicited AEs included pyrexia, flu like illness, headache and injection-site- related side effects (erythema, swelling, induration and pain).

In general, MV-CHIK vaccine had an acceptable tolerability profile. All adverse events observed were treatment emergent AEs and were recovered without any sequelae before or at study end.

The most frequently solicited AEs were headache (57.1%), injection side pain (50.0%), influenza like illness (45.2%), vaccination side pain (40.5%), fatigue (38.1%), nausea (31.0%), myalgia (26.2%) and arthralgia (23.8%). The most frequently related solicited AEs were injection side pain (50.0%), vaccination site pain (40.5%), headache (28.6%) and fatigue (23.8%).

Unsolicited AEs were AEs with none of the preferred terms of solicited AEs. 28 subjects (66.7%) had a total of 73 unsolicited AEs. Two subjects (4.8%) had two severe unsolicited AEs, five subjects (11.9%) had seven related unsolicited AEs and 19 subjects (45.2%) reported 33 unsolicited AEs where an action was taken. Two subjects (4.8%) reported two serious unsolicited AEs. The most frequently unsolicited AEs were nasopharyngitis (26.2%) and oropharyngeal pain (11.9%).

Special attention was directed to any occurrence of joint pain during the MV-CHIK study due to significant joint pathology caused by CHIKV. The subjects were asked to report any symptoms of joint pain in their subject diary and they were asked for any symptoms during each visit. Overall, 23.8% (10/42) of the subjects reported any signs of joint pain or arthralgia during the treatment period, 11.9% (5/42) of which were rated as related to the study treatment. In all 5 cases the joint pain was described as transient musculoskeletal pain, which was accompanied by flu like symptoms. Pain in the limbs associated with MV-CHIK injection was largely graded as mild (82%), was self-limiting and did not engender any withdrawals from the study. The rate of musculoskeletal pain decreased from 12% (n=5; 67% mild) at the first visit to 2% (n=1; 100% mild) at visit 5. No signs of inflammation were observed.

Severe and serious AEs occurred only for subjects treated with MV-CHIK. All serious AEs reported were non-local and unsolicited. Overall, seven severe AEs occurred (in six participants), of which five were solicited and related to vaccination including headache, local erythema, local induration, local pain and pyrexia.

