### 13.2 Safety Analysis

Solicited AEs (reactogenicity): Solicited local and solicited systemic AEs will be summarized for the 7 day period, by AE grade (mild, moderate, severe), by group and by dose. Solicited AEs will not be coded into MedDRA or assessed for relatedness. The number and percentage of subjects with AEs will be presented. Subjects who reported data for a solicited event at any time point during the time period summarized would be included in the denominator for that event. Thus, denominators for each solicited event will not include subjects who were missing all data for that event, during the time period summarized. P-values for AE rates for MV-CHIK vs. Priorix® (or equal control-vaccine), for the same schedule, will be provided in summary tables (pairwise comparisons).

Unsolicited AEs: Separately, the number and percentage of subjects with unsolicited treatment emergent adverse events (TEAEs), medically-attended AEs (MAEs) and serious adverse events (SAEs) will be presented for each treatment group overall and by system organ class/preferred term, and by AE grade, and relatedness. All SAEs and MAEs are also included in TEAE tables. Arthritis AEs, AEs of special interest (AESI), will be included in the TEAE tables. For unsolicited AEs, all subjects entered into the study who receive at least one vaccination will be included in the safety analysis based on the product received (“as treated”), for the time period summarized. P-values for AE rates for MV-CHIK vs. Priorix®, for the same schedule, will be provided in summary tables (pairwise comparisons).

Unsolicited AEs and concomitant diseases will be coded using the MedDRA coding dictionary; concomitant medications will be coded using the WHO Drug Dictionary.

Solicited and unsolicited AEs (local and systemic), MAE, SAE and AESI (arthralgia) will be recorded up to Visit 6 (day 224).

Safety analyses will be performed by means of descriptive measures. Laboratory values will be assigned a grade. Changes in laboratory values and grades as well as vital signs from study entry to end of treatment/follow up will be analyzed descriptively.

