			overall (mITT population)		
T-cell Ar	nalysi	S			
3.1.20	Х	Х	Number of subjects of functional Chikungunya virus specific T cells		
			by visit, treatment group and overall (mITT population)		
3.1.21	Х	Х	GMT for T cell immune by visit, treatment group and overall (mITT		
			population)		
3.1.22	х	Х	ANOVA with fixed factor treatment group for T-cells by visit (mITT		
			population)		
Measle	s Viru	s Sh	edding		
3.1.23		х	Number of subjects participating in measles virus shedding by		
			treatment group and overall (mITT population)		
3.1.24		х	Number of sample performed by visit, treatment group and overall		
			(mITT population)		

Based on: STAT03_A Statistical Analysis Plan

Version 5.0, Effective Date 16-Dec-2016

Confidential and intellectual property of Assign DMB. No part of this document or its contents may be duplicated, referenced, published or otherwise disclosed in any form or by any means without prior written consent of Assign DMB.

3.1.25		Х	Number of subjects with positive shedding results in urine by visit,	
			treatment group and overall (mITT population)	
3.1.26		Х	Number of subjects with positive shedding results in saliva by visit,	
			treatment group and overall (mITT population)	
3.2.1 -		х	Repeat the tables for the PP population	
3.2.26				
			Safety Analysis	
4.1		Х	Extent of Exposure (Safety population)	Study duration,
				Treatment duration
4.2	Х	х	Solicited Adverse Events ('Analysis' population)	AE, serious AE, severe AE, AE by severity
4.3	x	x	Unsolicited Adverse Events ('Analysis' population)	TEAE, serious TEAE, severe TEAE, TEAE related to study drug, medically attended TEAE, TEAE where an action was taken, TEAE of special interest (arthritis)
4.4	х	х	At least one unsolicited TEAE by SOC, PT, treatment group ('Analysis' population)	
4.5	х	х	At least one severe unsolicited TEAE by SOC, PT, treatment group ('Analysis' population)	
4.6	Х	х	At least one serious unsolicited TEAE by SOC, PT, treatment group ('Analysis' population)	
4.7	Х	х	At least one unsolicited TEAE related to study drug by SOC, PT, treatment group ('Analysis' population)	
4.8	х	х	At least one medically attended unsolicited TEAE by SOC, PT, treatment group ('Analysis' population)	
4.9	х	х	At least one unsolicited TEAE where an action was taken SOC, PT, treatment group ('Analysis' population)	
4.10	х	х	At least one unsolicited TEAE of special interest by SOC, PT, treatment group ('Analysis' population)	

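### The special-interest line counts only unsolicited arthritis although the protocol also names arthralgia, and no table counts each subject once for any joint event

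*SAP*

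**What the plan says.** Protocol 13.2 (Safety Analysis) labels the AESI twice, differently. On what goes into the tables: "Arthritis AEs, AEs of special interest (AESI), will be included in the TEAE tables". On what is collected, and for how long: "MAE, SAE and AESI (arthralgia) will be recorded up to Visit 6 (day 224".

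SAP 8.3 places its special-interest line under unsolicited events, as "at least one TEAE of special interest (arthritis". In SAP 10.1, Table 4.3 repeats that line and Table 4.10 is titled "At least one unsolicited TEAE of special interest by SOC, PT", again restricted to unsolicited events.

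Arthralgia sits on the other side of the split. SAP 8.3 states: "Solicited systemic AEs are the following: headache, fever, myalgia, limb discomfort, arthralgia, flu-like symptoms, nausea, vomiting, rash and excessive fatigue". Solicited events are summarised over 7 days, and "Solicited AEs will not be coded into MedDRA and no assessment of relatedness was performed".

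Protocol 11.2.4 names nausea/vomiting, headache, fatigue and myalgia as the diary's solicited systemic events, not arthralgia, though the list may not be exhaustive. It then asks separately for careful assessment of arthralgia. SAP 2.13.2 does list joint pain (arthralgia) as a diary symptom. SAP 2.17 says that no change to the analysis described in the protocol is intended.

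**The concern.** Joint symptoms are the disease-specific safety question for a chikungunya vaccine. Protocol 2.6 recalls transient arthralgia with an earlier live attenuated chikungunya vaccine and commits to monitoring for it. Protocol Table 2 schedules an arthralgia assessment at every clinic visit through Visit 6. The purpose of an AESI table is to gather the event of interest in one place. Here the line carrying that label would hold only unsolicited arthritis, and the joint symptom that the protocol tracks most closely would be spread over other tables by source. A reader who wants the number of subjects with any joint event by treatment group could not get it from a planned table. Adding rows would count some subjects twice.

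**Working it through.** **1. Phase 1 figures reproduced.** Protocol 2.4 reports that "23.8% (10/42) of the subjects reported any signs of joint pain or arthralgia during the treatment period".
- 10/42 = 0.2381, or 23.8%. Exact (Clopper-Pearson) 95% interval: 12.1% to 39.5%.
- Rated related: 5/42 = 0.1190, or 11.9%. Interval: 4.0% to 25.6%.

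Both percentages match the protocol.

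**2. Where each kind of joint event goes under the SAP.**
- *Joint pain within the 7-day diary.* Solicited under SAP 8.3. It appears in the summary of solicited events by symptom and severity (MV-CHIK vs control), in diary Tables 4.39, 4.40, 4.43 and 4.44, and in Figure 4.2. It does not reach the special-interest line of Table 4.3 or Table 4.10.
- *Joint pain starting after the diary.* The SAP gives no rule. If it is solicited by term, it falls outside the 7-day summary. If it is unsolicited, it reaches the SOC/PT tables but still misses an AESI line limited to arthritis. Either way it is not in the AESI count.
- *Joint pain found at a visit.* Tabulated by visit in Table 4.26 (SAP 8.7). Protocol 11.2.2 also requires reported symptoms to be recorded as adverse events, which leads back to one of the two routes above.
- *Arthritis reported as an unsolicited event.* Tables 4.3 and 4.10.

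Table 4.40 has an overall column across diary periods, but it covers diary data only. No listed table pools the sources.

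**3. Time outside the diary.** Groups A-D have three injections, so 3 × 7 = 21 diary days out of 224, or 9.4%. Within the 28 days after one injection, the period used in a secondary endpoint, the diary covers 7/28 = 25%. These are shares of calendar time, not of events; much post-vaccination joint pain may fall inside the diary.

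**4. Illustration of scale.** MV-CHIK subjects planned (protocol Table 1): 4 × 60 + 2 × 20 = 280. Assume that the Phase 1 rate carries over:
- any joint pain: 280 × 10/42 = 66.7, about 67 subjects (34 to 110 over the interval in step 1);
- rated related: 280 × 5/42 = 33.3, about 33 subjects.

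If the Phase 1 statement that no inflammation was seen is read as 0/42 arthritis, the upper 95% limit is 1 − 0.025^(1/42) = 8.4%. Zero among 280 would have an upper limit of 1 − 0.025^(1/280) = 1.3%. This contrast concerns the AESI line alone.

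**The case against.** The strongest reply is that the SAP follows the protocol. Of the two sentences in 13.2, the one about tables names arthritis; the arthralgia sentence concerns recording. That stands, so this is an unreconciled definition inside the protocol. A reader might infer that the SAP departed from a single clear AESI of arthralgia, but the text does not support that.

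Second, arthralgia is reported by symptom, severity and group in several tables and a figure. This also stands. A reader might infer that the joint signal as a whole would read near zero; the documents do not support this, because only the line labelled arthritis could do so.

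Third, it may seem that solicited arthralgia could never be shown by preferred term or causality. SAP 8.3 says that solicited events are neither coded nor assessed for relatedness. Yet Listing 4.3 has a preferred-term field covering solicited types, and Listing 4.8 has a causality field for systemic events. The SAP is inconsistent here, so the absolute reading fails.

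Fourth, the Phase 1 contrast is weak. The 42 include control subjects, the doses and formulation differed, and the diary ran two weeks. The five related cases were transient musculoskeletal pain with flu-like symptoms. No arthritis count is given.

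Fifth, pooling common short-lived arthralgia with arthritis could bury a rare arthritis case. This is a fair reason to keep arthritis visible separately, but not a reason to have no pooled count.

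**Conclusion.** The point holds as one of definition and completeness. The protocol gives the AESI two names, and the SAP tabulates one of them, among unsolicited events only. As written, the AESI line omits an event that the protocol itself labels AESI and records to day 224. No planned table counts a subject once for any joint event through Visit 6, and the class of arthralgia starting after the diary is undefined.

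The size in this trial cannot be derived from the documents. The only guide is the Phase 1 rate of 23.8% (11.9% related), which would mean about 67 (about 33 related) of 280 MV-CHIK subjects if it carried over. That figure is illustrative, for the reasons given above, and a zero arthritis count in Phase 1 is an inference. Most of these subjects could still appear in the solicited and diary tables; what they lack is a place in the AESI count.

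**What to change.** - **Definition.** Reconcile the two sentences in protocol 13.2 with SAP 8.3 into one AESI definition with named terms: arthralgia/joint pain, joint swelling, arthritis. State that joint events starting after day 7 are included.
- **Table.** Add one table that counts each subject once for any joint event from any source (diary, adverse event record, visit assessment) through Visit 6, by group, severity and onset window. Keep arthritis as a separate row, and show relatedness where it was recorded.
- **Comparison.** Compare MV-CHIK with same-schedule control for groups A-D only. M1 and M2 have no control recipients on their schedule and should be descriptive.
- **Coding.** Use a fixed symptom term for solicited arthralgia in this table. The rule against MedDRA coding of solicited events can then stay as it is.

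The cost is one extra table, a wording change in SAP 8.3 and a short one in protocol 13.2. No new data are needed: the visit assessments and diary entries are already planned, and the systemic event listings hold start date, end date and severity. The reported AESI rate will be higher, which the table's footnote should explain.

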8.4 Laboratory Parameters

The following laboratory parameters are analyzed throughout the study at Screening, Visit 3 (Day 56), Visit 6 (Day 224) and ET visit. The laboratory parameters will be converted to the standard units provided in the table below:

SAP (MV-CHIK-202, FINAL 3.0, 09-May-2018)

Page 33 of 47

Based on: STAT03_A Statistical Analysis Plan

Version 5.0, Effective Date 16-Dec-2016

Confidential and intellectual property of Assign DMB. No part of this document or its contents may be duplicated, referenced, published or otherwise disclosed in any form or by any means without prior written consent of Assign DMB.

Туре	Parameter	Standard Unit
Hematology	Hemoglobin	g/L
Hematology	Hematocrit	%
Hematology	Erythrocytes	T/L
Hematology	Leukocytes	G/L
Hematology	Platelets	G/L
Hematology	Neutrophils	G/L
Hematology	Basophils	G/L
Hematology	Lymphocytes	G/L
Hematology	Monocytes	G/L
Hematology	Eosinophils	G/L
Hematology	Eosinophils	G/L
Hematology	Neutrophils/Leukocytes	%
Hematology	Lymphocytes/Leukocytes	%
Hematology	Monocytes/Leukocytes	%
Hematology	Eosinophils/Leukocytes	%
Hematology	Basophils/Leukocytes	%
Clinical chemistry	Bilirubin	µmol/L
Clinical chemistry	Creatinine	µmol/L
Clinical chemistry	Alanine Aminotransferase (ALT)	U/L
Clinical chemistry	Aspartate Aminotransferase (AST)	U/L
Clinical chemistry	Sodium	mmol/L
Clinical chemistry	Calcium	mmol/L
Clinical chemistry	Potassium	mmol/L
Clinical chemistry	Alkaline phosphatase	U/L
Coagulation	Prothrombin time (PT)	%

Confidential and intellectual property of Assign DMB. No part of this document or its contents may be duplicated, referenced, published or otherwise disclosed in any form or by any means without prior written consent of Assign DMB.

Туре	Parameter	Standard Unit
Coagulation	Activated partial thromboplastin time (aPTT)	S
Coagulation	Prothrombin Time absolute	S
Coagulation	Fibrinogen	g/L

8.4.1 Tables of Hematology, Clinical chemistry and Coagulation

The following tables will be provided:

- Separate tables will be provided for hematology, clinical chemistry and coagulation.
- The number of available samples as documented in the eCRF (item "Has blood sample been drawn" is set to "yes") will be tabulated separately by parameter and by visit (frequency statistics).
- Absolute values for all laboratory parameters will be tabulated by visit (summary statistics). •
- Absolute changes from screening (difference: value after screening value at screening) for all laboratory parameters will be tabulated by visit (summary statistics).

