**STATISTICAL METHODS:**

The primary immunogenicity analysis will compare the PRNT50 antibody geometric mean titer (GMT) 28 days after one or two immunizations in the per-protocol (PP) analysis population between the treatment groups. GMTs and GMT ratios will be estimated by applying an analysis of variance including the factor vaccination group and adjusting for multiple comparisons according to Tukey-Kramer. This will be done using log-10 transformed data and taking the anti-log of the resulting point estimates the least squares means, least squares means differences and the corresponding 95% CIs.

All subjects entered into the study, who receive at least one vaccination, will be included in the safety analysis. For solicited local and solicited systemic AEs, the number and percentage of subjects with AEs will be summarized for the 7 day diary period, by AE grade (mild, moderate, severe), by group and by dose. Relatedness will not be assessed for solicited AEs.

For unsolicited AEs, the number and percentage of subjects with treatment emergent adverse events (AEs) and serious adverse events (SAEs) will be presented for each treatment group overall and by system organ class/preferred term, and by AE grade, and relatedness. For unsolicited AEs, all subjects will be included in the safety analysis based on the product received (“as treated”) for the time period summarized. Changes in laboratory values will be analyzed descriptively by grade and by group from study entry until time point of assessment.

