### **11.2.6 Laboratory parameters**

The following laboratory parameters will be assessed at time points specified in Table 2 and graded according to the FDA Guidance for Industry: Toxicity Grading Scale for Healthy Adult and Adolescent Volunteers Enrolled in Preventive Vaccine Clinical Trials (Sept. 2007).

The following parameters will be analyzed by local laboratories according to the applicable laboratory SOP:

- Hematology: hemoglobin, hematocrit, erythrocyte count, differential white blood count, platelets.
- Chemistry: creatinine (>1.7 mg/dL), potassium, sodium, calcium, AST, ALT ( $\geq 2.6$  ULN), alkaline phosphatase, bilirubin
- Coagulation parameter: prothrombin time (PT), activated partial thromboplastin time (aPTT), fibrinogen
- Virology: HIV 1/2 Ab if not done within 30 days before screening and HBs-Ag, anti-HBc-Ab and anti-HCV-Ab
- Urinalysis: a standard urine test stick for determining pH-value, glucose, protein, bilirubin, urobilinogen, red blood cells, white blood cells, nitrite, ketone and specific gravity will be used and clinical relevant findings will be noted in the source data and in the eCRF.

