**Table 10 Blood sample collection:**

Test	Type of Vials	Volume	Collections
Virology (HIV, HBV, HCV) (all sites)	serum	8 – 10 mL	1x
Immunogenicity 1 and Measles Serology (all sites)	serum	2x 8 - 10 mL	5x (A-D), 7x (M1, M2)
Immunogenicity 2 (all sites except sites in Vienna)	serum	2x 8 -10 mL	5x (A-D), 7x (M1, M2)
T cell Analysis (all sites in Vienna)	(citrate tubes) PBMCs	3x 8-10 mL once 6x 8-10 mL	5x (A-D), 6x (M1, M2)
Shedding whole blood (only AKH Vienna)	EDTA	2 - 3 mL	6x (shedding analysis, A-D only)
Hematology (all sites)	EDTA	3 - 5 mL	3x
Coagulation (all sites)	citrate tubes	3 - 5 mL	3x
Clinical chemistry (all sites)	serum	8 - 10 mL	3x

The total blood volume that will be collected during the entire study:

Sites outside Vienna:	treatment group A, B, C, D: 210 – 270 mL treatment group M1 and M2: 274 – 350 mL
Site AKH in Vienna:	treatment group A, B, C, D: 286 – 368 mL treatment group M1 and M2: 330 – 420 mL
Site Tropical Medicine Vienna:	treatment group A, B, C, D: 274 – 350 mL treatment group M1 and M2: 330 – 420 mL

Laboratory values deviating from the normal ranges will be evaluated by the investigator according to the FDA Guidance for Industry. The values will be graded (mild, moderate, severe) according to the values provided. Clinically relevant deviations have to be reported as adverse events.

NCR = not clinically relevant deviation

CR = clinically relevant deviation

NA = not assessable - laboratory error.

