### **Treatment group stopping rules**

If four or more subjects in a treatment group experience a treatment related grade 3 suspected adverse reaction (SAR) or laboratory abnormality, or one or more subjects in a treatment group experience a treatment related grade 4 SAR or laboratory abnormality, the study will be suspended pending an unblinded safety review of those subjects by the DSMB. This safety review might lead to the recommendation to discontinue a treatment group.

In case a treatment group has to discontinue the clinical study prematurely for any reason, the concerned subjects should be asked to perform an early termination visit. Additionally, women of childbearing potential will be followed up by a phone call, 3 months after the last vaccination to ensure no pregnancy occurred within this period as confirmed by a urine pregnancy test provided by the investigator.

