The statistical analysis plan is based on the final study protocols for Austria (Version 1.5; 24-Nov-2016) and Germany (Version 1.6; 19-Apr-2017). No changes in the conduct of the planned analysis as described in the CSP are intended.

However, the time point of the Preliminary Analysis was moved forward to August 2017. The Preliminary Analysis was initially planned to take place after all subjects completed Visit 3.

Page 21 of 47

3. **OVERALL STUDY INFORMATION**

Treatment groups for the preliminary analysis as well the final analysis are defined in section 2.3. Overall study information analysis will be prepared for the:

- Preliminary analysis: mITT population. •
- Final analysis: Safety, mITT and PP population. •

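### The protocol plans a laboratory analysis by toxicity grade and group; the SAP tabulates no laboratory grade and does not declare the omission

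*SAP*

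**What the plan says.** **Protocol.** Safety laboratory parameters are a secondary endpoint (4.1.2).

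- Section 11.2.6 says that the parameters will be "graded according to the FDA Guidance for Industry: Toxicity Grading Scale for Healthy Adult and Adolescent Volunteers". The text after Table 10 adds: "The values will be graded (mild, moderate, severe) according to the values provided".
- Section 13.2 says "Laboratory values will be assigned a grade" and then: "Changes in laboratory values and grades as well as vital signs from study entry to end of treatment/follow up will be analyzed descriptively".
- The synopsis (Statistical Methods) supplies the breakdown: "Changes in laboratory values will be analyzed descriptively by grade and by group from study entry until time point of assessment".

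**SAP.** Section 8.4.1 plans the number of available samples, then "Absolute values for all laboratory parameters will be tabulated by visit (summary statistics"), then absolute change from screening in the same form. Section 2.6 defines summary statistics as N, mean, SD, median, quartiles, minimum and maximum. In section 10.1, Tables 4.12 to 4.18 add treatment group to each of these. Section 8.4.2 plans listings of values outside normal limits, with clinical relevance and causal relationship. On departures from the protocol, section 2.17 states: "No changes in the conduct of the planned analysis as described in the CSP are intended". The only exception it gives is the earlier date of the preliminary analysis.

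**The concern.** An analysis that the protocol specifies has no counterpart in the SAP, and the SAP says nothing has changed. A programmer working from section 10 will produce no laboratory table by grade, and a reader of the study report will not learn from the SAP or the report why.

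A laboratory safety question in a vaccine dose-finding trial is usually how many subjects in each group reached each grade. The protocol itself treats these grades as important. Its group-level rule in 11.3 is worded in them ("If four or more subjects in a treatment group experience a treatment related grade 3 suspected adverse reaction (SAR) or laboratory abnormality"), and its individual discontinuation rule also refers to grades 3 and 4. One secondary objective is to choose a dose and schedule for Phase 3, and a count per grade and group is a natural part of the safety comparison behind that choice.

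**Working it through.** The plan gives no figure on this point, so there is none to reproduce. The check sets the two documents side by side.

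1. **Is grading specified?** Yes. Protocol 11.2.6 names the scale, 13.2 says grades are assigned and changes in grades described, and the synopsis says by grade and by group.
2. **Do the SAP tables carry a grade?** No. Table 4.12 counts samples, 4.13 to 4.15 give absolute values, and 4.16 to 4.18 give absolute changes. All are by treatment group, and the last six also by parameter and visit. Group is therefore covered; grade is not.
3. **Do the SAP listings carry a grade?** No. Listings 4.15 to 4.17 hold value, unit, normal range, clinical relevance, causal relationship and change from screening.
4. **Does grading appear elsewhere in the SAP?** Grades 1 to 4 are defined in 2.13.1 and 2.13.2, but only for diary tolerability symptoms.
5. **Do the adverse event tables supply the count?** Only in part. Under protocol 11.2.6 a deviation becomes an adverse event if it is clinically relevant, and 14.1.2 defines a laboratory adverse event by the need for active management. Severity in 14.2 is rated by interference with daily activities, not by laboratory cut-offs. A graded abnormality without symptoms may be rated mild or may not reach these tables.
6. **Can the count be recovered from the summary statistics?** No. Take a group of 60, the planned MV-CHIK size in each of A to D.
   - Under the usual definition the upper quartile is the average of the 45th and 46th ordered values (0.75 × 60 = 45). The 60 − 46 = 14 larger values do not affect it. If the cut-off lies between the 46th value and the maximum, the upper quartile and maximum are compatible with anything from 1 to 14 subjects beyond it. Mean and SD would differ between these cases but do not give the number.
   - A maximum (or minimum) beyond a cut-off shows only that at least one case occurred. For an assumed true rate p, that probability is 1 − (1 − p)^60 and the expected count is 60p:

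| Assumed rate p | P(at least one in 60) | Expected count |
|---|---|---|
| 1% | 45% | 0.6 |
| 2% | 70% | 1.2 |
| 5% | 95% | 3 |
| 10% | 99.8% | 6 |

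The rates are illustrative; the documents give none. Between 2% and 10% the expected count rises fivefold, while the chance of seeing an extreme only moves from 70% to 99.8%.

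**The case against.** The strongest reply is that little information is lost. The SAP's summary statistics are not confined to means. They include the minimum and maximum of values and of changes, by treatment group, so a markedly abnormal subject would show. Each out-of-range value is listed with treatment group, clinical relevance and causal relationship, so affected subjects can be found and counted by hand. Clinically relevant deviations also appear as adverse events, with subject counts by preferred term and group, including tables of severe and of related events.

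All of that stands, and it rules out some stronger conclusions. A reader might infer that severe laboratory abnormalities would go unreported, or that the report could show no laboratory difference while one dose group had several. The documents do not support either: the extremes, listings and adverse event tables remain.

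A reader might also infer that the stopping rules are undermined. They are not. Those rules operate during conduct, through investigator assessment and unblinded DSMB review, and end-of-study tables do not drive them. The group rule also counts treatment-related abnormalities, so a grade table without causality would not reproduce its count.

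Finally, the protocol asks for a descriptive analysis of grades and of changes in them. It does not require a particular layout such as a shift to worst grade.

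What the reply does not supply is the count by grade. Counting from listings would mean grading each line by hand against a scale the SAP does not cite. It would also assume that every gradable value falls outside the local normal range, which the documents do not establish.

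**Conclusion.** The point holds as an undeclared omission. The protocol plans a descriptive laboratory analysis by toxicity grade and group; the SAP contains no laboratory grade in any table or listing; and SAP 2.17 does not acknowledge the difference. The number of subjects at each laboratory grade is therefore not tabulated.

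The consequence is moderate. Primary immunogenicity inference is untouched, and individual abnormal values remain traceable. The loss is a direct comparison of graded abnormalities between groups, for a secondary safety endpoint.

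The conclusion rests on comparing the text of the two documents, not on any assumed event rate. The grading scale's cut-offs are not printed in either document, so no particular value can be assigned a grade here.

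A related inconsistency needs attention. For laboratory values, protocol 11.2.6 names three categories (mild, moderate, severe), while 11.3 refers to grades 3 and 4. The passages must be reconciled before the table categories can be fixed.

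**What to change.** - **Tables.** Add to SAP 8.4.1 and section 10.1, for the Safety population, the number and percentage of subjects at each laboratory grade, by parameter, visit and treatment group. Include change from screening grade, for example as a shift to the worst post-baseline grade over Day 56, Day 224 and early termination. A shift table is one convenient form; a grade-by-visit table that also shows the screening grade would meet the protocol's wording too.
- **Listings.** Add a grade column to Listings 4.15 to 4.17.
- **Derivation.** Cite the scale named in protocol 11.2.6, and state whether the tabulated grade is the investigator's or is derived from the recorded value.
- **Categories.** Reconcile the grade categories in protocol 11.2.6 with those in 11.3, and use the result in the tables.
- **Alternative.** If the sponsor does not want the graded analysis, declare and justify its omission in SAP 2.17.

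If grades are derived from the recorded values, the cost is SAP text and table programming, with no new assessments or samples.
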